### **Data analysis strategy**

Text responses from participants' feedback on the intervention overall will be analysed using content analysis to identify helpful aspects of the intervention and areas for improvement.

Quantitative data (outcome measures and acceptability ratings) will be screened for outliers and missing values, and descriptive statistics will be conducted for all variables. The data will be tested for the assumption of normality. Paired t-tests will be used to test for differences in participants' psychological outcome measures before and after the intervention. This information will also be used to calculate effect sizes ( $d_z$ ) for changes in scores on each outcome measure. Intention-to-treat and completer analyses will be carried out.

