## **Aims**

The study aims to explore whether the online compassion-based guided self-help is perceived as acceptable to people with heterogeneous skin conditions, in terms of retention rates and explicit feedback. The study also aims to investigate the feasibility of providing online compassion-based self-help and email guidance. Changes in depression, self-compassion and skin-related distress will be assessed to give an estimate of likely effect sizes for future research.

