### **Sample size**

Although all clinical trials require sample size justification, formal sample size calculations are not necessarily appropriate for feasibility trials (Billingham, Whitehead, & Stevens, 2013). In this study, qualitative acceptability data will be used for further development of the intervention as necessary. Quantitative data (such as feedback ratings and changes in depression) will inform future research about the acceptability of the intervention in its current form and provide an estimate of the effect size for depression. A minimum sample size of 12 can be justified based upon precision of the estimates to be used in future research (Julious, 2005), although extra participants need to be recruited to allow for attrition. A meta-analysis of internet-based CBT found that attrition was 48% at the 75th percentile of studies (Andrews et al., 2018). To allow for up to 48% attrition, it will be necessary to recruit 23 participants to provide the minimum sample size of 12.

The maximum sample size is dictated by the available resources to facilitate the intervention. Based on clinical experience of providing email and telephone guidance to patients undertaking cCBT, it is expected that providing email support will take around 10 minutes per week per patient on average. Given the researcher's working pattern, up to nine hours per week could be allocated for directly facilitating the intervention (approximately half of the researcher's part-time hours). This leads to a maximum of 54 ( $[9 \times 60]/10$ ) participants that can be provided with email support at any one time. Although it would be possible to include more participants in the study due to the rolling nature of recruitment, there are diminishing returns on the value of increasing the sample size, as gains in the precision of estimates become less pronounced (Hertzog, 2008; Julious, 2005). It therefore seems logical to set 54 participants as the maximum sample size for the study.

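### The plan reports d_z with no small-sample correction or interval; from completers it overstates a non-zero change on average, by 7.5% at 12 pairs and 1.4% at 54

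*Combined protocol and SAP*

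**What the plan says.** The Data analysis strategy states: "Paired t-tests will be used to test for differences in" the psychological outcome measures before and after the intervention. It continues: "This information will also be used to calculate effect sizes", with d_z given as the index for each outcome measure. It then says: "Intention-to-treat and completer analyses will be carried out". The section does not mention a small-sample correction, a confidence interval for the effect size, or how missing outcomes enter the intention-to-treat analysis.

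The Aims give the purpose of these figures: "Changes in depression, self-compassion and skin-related distress will be assessed to give an estimate of likely effect sizes for future research".

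The Sample size section sets the range of n. At the lower end, "A minimum sample size of 12 can be justified based upon precision of the estimates to be used in future research". On attrition it says "To allow for up to 48% attrition", and then "it will be necessary to recruit 23 participants to provide the minimum sample size of 12". At the upper end, "It therefore seems logical to set 54 participants as the maximum sample size for the study".

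**The concern.** d_z is the mean paired change divided by the standard deviation of the paired changes. When that standard deviation comes from a few people, the ratio is on average further from zero than the true standardised change. The bias depends only on the degrees of freedom and is a fixed proportion of the true value. It is largest at the smallest sample, and 12 is a size the plan accepts in advance.

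The effect size is an intended product of this study, since both the Aims and the Sample size section hand it to future research. An analyst who follows the plan literally would report the uncorrected statistic without an interval. A later team that took the figure as its target would plan a study that is somewhat too small, and the report would not show how uncertain the figure is.

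This is separate from the choice of denominator. Any standardised change whose standard deviation is estimated from so few people has the same kind of bias.

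**Working it through.** **Inputs.** From the Sample size section: minimum 12, attrition 48%, recruitment 23 for the minimum, maximum 54. From the Data analysis strategy: paired t-tests and d_z, so the degrees of freedom are m = n − 1. The plan assumes no value of d_z. For illustration I use 0.64, the meta-analytic d quoted in the background section on compassion-based self-help. That value is not itself a d_z, and the percentages below do not depend on it.

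**The plan's own figure.** 12 / (1 − 0.48) = 12 / 0.52 = 23.08, which the plan rounds to 23 (23 × 0.52 = 11.96). The figure is reproduced. The same attrition at the maximum gives 54 × 0.52 = 28.08, or about 28 pairs. The plan states no figure for bias or precision of the effect size to reproduce.

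**Bias factor.** For normally distributed changes with true standardised change δ, the average of d_z is δ / J(m), where

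J(m) = Γ(m/2) / [√(m/2) × Γ((m−1)/2)].

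At n = 12, m = 11: Γ(5.5) = 52.343, √5.5 = 2.3452, Γ(5) = 24, so J = 52.343 / (2.3452 × 24) = 0.930 and 1/J = 1.0753. The usual approximation 1 − 3/(4m − 1) = 1 − 3/43 = 0.930 agrees.

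If a later study used d_z directly as its target, the required n scales as 1/d². The planned n would then be J² times what is needed, a shortfall of 1 − J².

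| Pairs | J | Average overstatement, 1/J − 1 | Shortfall, 1 − J² |
|---|---|---|---|
| 12 (accepted minimum) | 0.930 | 7.5% | 13.5% |
| 23 | 0.965 | 3.6% | 6.8% |
| 28 (54 less 48%) | 0.972 | 2.9% | 5.5% |
| 54 (maximum, no attrition) | 0.986 | 1.4% | 2.8% |

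**Size against sampling error.** The sampling standard deviation of d_z comes from the noncentral t distribution.

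- n = 12, true 0.64: the average d_z is 0.64 × 1.0753 = 0.688, so the bias is 0.048 against a standard deviation of 0.359. The bias is 0.048 / 0.359 = 13% of one standard deviation.
- n = 28: the bias is 0.018 against 0.218.
- n = 54: the bias is 0.009 against 0.153.
- An observed d_z of 0.64 from 12 pairs has an exact 95% interval of about 0.00 to 1.25.

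**Limits on direction.** If the true change is zero, the bias is zero. At n = 12 and a true value of 0.64, a single estimate still falls below the truth about 48% of the time.

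For the intention-to-treat set, suppose 23 are recruited, 12 complete, and the 11 others are assigned no change. That rule is an assumption, since the plan states none. With a completers' true value of 0.64, simulation gives an average d_z of about 0.43, so the net error relative to 0.64 would be downward.

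**The case against.** - **The 7.5% is a floor case.** This stands. Twelve pairs result from recruiting only 23 and losing 48%, the 75th-percentile attrition in the cited meta-analysis. The Estimated timescale section starts from about 59 recruits a month in an earlier study and expects somewhat fewer here, so samples nearer the maximum are plausible. With 54 recruits and the 66% median retention cited under the acceptability criteria, about 36 pairs would remain (54 × 0.66 = 35.6) and the bias would be about 2.2%.
- **No correction is mentioned, but none is excluded.** This also stands. However, d_z is the uncorrected statistic by name, and a reader following the plan would report it.
- **A later user can apply J from d_z and n.** True, but that does not make the reported value unbiased, and it relies on someone else noticing.
- **Sampling error dominates and the main aims are acceptability and feasibility.** Correct, and this is why the point is minor. It also means that correcting the point estimate without an interval would leave the larger uncertainty unreported.

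Three stronger readings might be inferred, and the documents do not support them:

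- **Every reported effect size will be too high.** The bias is an average over repeated studies and vanishes when there is no change.
- **The same inflation applies in both analysis sets.** The intention-to-treat set may contain more people, and its net direction depends on a missing-data rule the plan does not give.
- **A specific per-arm shortfall for a two-group trial.** This is a single-arm pre–post study, and d_z, which depends on the pre–post correlation, is not a between-group d. Only the relative 1/d² scaling holds, and only if a later team uses the value directly as its target. The plan says only that the estimates will inform future research.

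**Conclusion.** The point holds as a minor reporting improvement, not a design flaw. For completers, the planned d_z overstates the absolute standardised change on average by 1.4% to 7.5% across the plan's range of 54 down to 12 pairs. This assumes roughly normal change scores, a non-zero true change, and that no unstated correction is intended. A study that took the value directly as its target would be undersized by up to about 13.5% at 12 pairs and 5.5% at 28. The bias is about an eighth of one sampling standard deviation at 12 pairs for a true 0.64. No direction can be claimed for the intention-to-treat estimate until its handling of missing outcomes is stated.

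**What to change.** In the Data analysis strategy, replace the effect-size sentence with wording such as: *For each outcome and each analysis set, the standardised change will be reported as g_z = J(n − 1) × d_z, where n is the number of participants in that analysis (J = 0.930 at n = 12), with a 95% confidence interval.* In the Aims and the Sample size section, name the corrected value and its interval as the estimate offered to future research. If the interval is the exact one from the noncentral t distribution, it already refers to the true standardised change and should not itself be multiplied by J.

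The cost is one multiplication and one interval per effect size, plus a sentence in the plan. No extra participants, data or design change are needed. The correction stays valid at any n reached, because J approaches 1 as n grows, and fixing it now avoids choosing between d_z and g_z after the results are seen. The downside is a slightly less favourable reported effect: an observed 0.64 becomes 0.930 × 0.64 = 0.60 at 12 pairs, and 0.986 × 0.64 = 0.63 at 54.

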In a review of self-help for people with visible differences, Muftin and [name] (2013) identified five studies with people with skin conditions. The only study that used an intervention specifically developed for people with a skin condition (psoriasis) found that it was not effective for depression (Bundy et al., 2013). This intervention was a computerised CBT programme designed for people with psoriasis. The authors suggested that the relatively low level of depression in the sample could have contributed to the lack of significant effect on depression. In addition, the study suffered from a high attrition rate (43% in the intervention arm), which suggests a problem with acceptability of the intervention. Two further studies investigated interventions designed for people with visible differences, which could potentially be used by people with skin conditions (Bessell et al., 2012; Newell & Clarke, 2000). Both interventions focused on addressing social anxiety, and while some improvements in depression were also found, most of the interventions' content would not be relevant for individuals with skin conditions for whom depression was the primary psychological

problem. Two other studies in the review investigated the effect of generic self-help interventions for depression in samples of people with skin conditions. One of these studies found that Mindfulness-Based Stress Reduction did not reduce depression among people with psoriasis (Jackson, 2006). In the other study, two techniques based on Compassionate Mind Training (Gilbert & Irons, 2005) were investigated with people with acne (Kelly, Zuroff, & Shapira, 2009). Both self-soothing and attack-resisting self-help reduced shame at two weeks compared to the control, but only the attack-resisting intervention reduced depression. The results of this review indicate that there is a need to develop interventions for depression in people with skin conditions.

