week after completing the baseline measures participants will receive an automated email inviting them to access the second session of the intervention. Automated emails will continue to be sent in this way, with homework reminders and links to subsequent sessions. The emails will also invite the participant to contact the researcher if they require further support with the self-help materials. The researcher will respond to any such emails individually. One week after the last session participants will be invited to provide feedback via Qualtrics about the guided self-help intervention overall, and to complete the outcome measures again.

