## Ethical issues

**Ethical approval.** The proposal, information sheet, consent form, measures and intervention exercises for the current study will be sent to the University of Sheffield Department of Psychology Research Ethics Sub-Committee for approval through the online ethics application system. In addition, the University of Sheffield's research governance procedure will be followed, including completion of the 'Risk Assessment Checklist for University Sponsored Human-Interventional Studies' and public registration of the study on 'ClinicalTrials.gov'.

**Informed consent.** All potential participants will read an information sheet (see Appendix A) and complete a consent form (see Appendix B) online prior to taking part in the study. They will have the opportunity to ask the researcher any questions about their participation in the study via email. The researcher's email address will be provided on the information sheet.

**Participant withdrawal.** Participants will be able to withdraw from the study at any point until their data are anonymised. Participants will be informed of this on the information sheet and may contact the researcher by email to request that their data is destroyed should they subsequently wish to withdraw from the study.

Eight of the guided self-help emails will be automatically sent from Qualtrics based on completion of the baseline measures. If any participants contact the researcher to withdraw from the study, that participant's Qualtrics data will be exported (for ITT analyses) and then the participant's contact details will be deleted from Qualtrics so that further automatic emails are not sent to that participant.

**Adverse effects.** As with all psychological interventions, there is a risk that taking part in this study may raise participants' awareness of pre-existing distressing thoughts and feelings, leading to some distress during or after taking part in the study. Participants will be made aware of this possibility prior to taking part in the study via the information sheet (see Appendix A). The information sheet will also provide participants with signposting information for mental health support (e.g. the Samaritans) and advise them to speak to their GP if necessary. In addition, if

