participants advise the researcher of any adverse effects via email, the researcher will be able to re-iterate options for further support as appropriate. The researcher previously worked in primary care mental health services for five years, providing guided self-help to people with depression and anxiety disorders, and is therefore experienced in dealing with emotional distress and signposting appropriately. If necessary, the researcher will discuss concerns with her primary supervisor, who is a clinical psychologist.

**Confidentiality.** Participants will be informed that their data will be kept confidential and that they will not be personally identifiable in any results of the study. Unique identification numbers will be used throughout the data sets. A data file will be created to contain participants' details and their identification numbers, for matching up quantitative data over time and to allow the destruction of data should participants wish to withdraw from the study. This data file will be password-protected and kept separately from the rest of the participants' data.

Spreadsheets containing participants' names and email addresses will also be created in order to administer the study—for sending emails on the correct dates and tracking participants' logins. No sensitive quantitative data will be kept in these spreadsheets, only dates. These spreadsheets will also be password-protected and kept separately from outcome measures and feedback data. Once data collection is complete, participants' names and email addresses will be replaced with their unique identification numbers.

Participants will be required to log into the study website solely to track user logins for the purpose of monitoring participants' engagement with the intervention from week to week. Participants will log into the website with a username (usually their first name) and password that has been allocated to them by the researcher.

Participants will not be asked to provide any data via the study website, nor will they be able to access any other participants' details. No-one except the researchers involved in the study will have access to participants' contact details.

**Data protection.** Personally identifiable digital data will be stored securely as described above, on the lead researcher's university filestore. The lead researcher will be

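### Do the withdrawal wording and the lack of a rule for missing post scores empty the promised intention-to-treat analysis of meaning?

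*Combined protocol and SAP*

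**What the plan says.** Data analysis strategy: "Paired t-tests will be used to test for differences" between the scores before and after the intervention, and d_z is computed from the same data. The section adds that "Intention-to-treat and completer analyses will be carried out". Missing values are to be screened for; nothing further is said about them.

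Procedure: one week after the last session, participants are invited "to complete the outcome measures again". This is the only outcome assessment after baseline.

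Sample size: "To allow for up to 48% attrition, it will be necessary to recruit 23 participants to provide the minimum sample size of 12". The maximum is 54.

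Ethical issues, Participant withdrawal: participants may email the researcher "to request that their data is destroyed should they subsequently wish to withdraw from the study". The next paragraph concerns stopping the automatic emails. It says that a withdrawing participant's "Qualtrics data will be exported (for ITT analyses") before the contact details are deleted. Under Confidentiality, a linking file is kept partly "to allow the destruction of data should participants wish to withdraw from the study".

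Acceptability and feasibility criteria: the thresholds are 66% logging in during week six, 90% logging in during week one, and at most 120 minutes of guidance per patient. None concerns an outcome score.

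**The concern.** A paired t-test drops anyone without a second score. If completer means having that score, and nothing is filled in, the intention-to-treat and completer results are one number under two labels. If completer means finishing the sessions, the intention-to-treat figure still leaves out people with no post score.

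The observed pairs describe everyone enrolled only if dropouts change as much as completers. The plan gives reason to doubt that. Retention is one of its measures of acceptability, and it comments on high attrition in an earlier psoriasis trial with the words "which suggests a problem with acceptability of the intervention". If dropouts improve less, d_z is too large, and a later study sized on it is too small. Supplying effect sizes for future research is a stated aim.

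The withdrawal text adds a second worry. One paragraph exports the data of any participant who withdraws; another links withdrawal with destruction. Destruction cannot be undone, so a real conflict would need settling before the first consent.

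**Working it through.** **1. The plan's own figures.** 12 / (1 − 0.48) = 23.08, and 23 × 0.52 = 11.96, so 23 is right to within rounding (strictly rounded up, 24). The maximum is 9 × 60 / 10 = 54.

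**2. People without a post score.** At 48%: 0.48 × 23 = 11 and 0.48 × 54 = 26. At 34%: 0.34 × 23 = 8 and 0.34 × 54 = 18. The 34% assumes that the 66% median retention cited for logins also applies to the post questionnaire. The 48% is a ceiling, taken from the 75th percentile of studies.

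**3. What the two analyses would show.** The plan gives no expected d_z, so 0.64 is assumed for completers (the average effect quoted in the introduction for compassion-based interventions), with 0.3 to 1.0 as the range. Scale the SD of change to 1, and let m of N people have both scores.

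- Observed pairs: d_z = 0.64, n = m.
- Baseline carried forward (zero change for the rest): mean = m·d/N; SD² = [(m − 1) + m·d² − N·mean²]/(N − 1).
- With m = 12, N = 23: mean = 12 × 0.64/23 = 0.334; SD² = (11 + 4.915 − 2.564)/22 = 0.607; SD = 0.779; d_z = 0.334/0.779 = 0.43.
- With m = 28, N = 54: d_z = 0.42.
- For m = 12, N = 23 and completer d_z of 0.3, 0.5, 0.8 and 1.0: 0.22, 0.35, 0.51 and 0.60.

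So the two analyses coincide only if nothing is filled in and completer means having a post score.

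**4. The value for everyone enrolled.** Let q be the loss and f the dropouts' mean change as a share of the completers', with equal SD. Then d_z = d(1 − q + qf)/√(1 + q(1 − q)(1 − f)²d²). With d = 0.64 and q = 0.48:

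| f | d_z, all enrolled |
|---|---|
| 1 | 0.64 |
| 0.5 | 0.48 |
| 0 | 0.32 |

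Observed pairs report 0.64 in every row. The carried-forward d_z in the same closed form is 0.333/√0.622 = 0.42. That is too low at f = 1 and somewhat too high at f = 0, because the zeros shrink the SD. Dividing the no-change mean by the completers' SD gives 0.52 × 0.64 = 0.33.

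**5. Against sampling error.** With 12 pairs and d_z = 0.64, t = 0.64 × √12 = 2.22, and the 95% interval for d_z is about 0.00 to 1.25. It contains every value in the table.

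**6. The withdrawal sentences side by side.** The destruction sentence says what a participant may ask for. The linking-file sentence says what the file makes possible. Neither orders destruction whenever someone withdraws. The export sentence sits in a paragraph about switching off automatic emails, and exporting first does not prevent destruction later on request. Read together: keep by default, destroy if asked. The Sample size paragraph only inflates recruitment for attrition and says nothing about who belongs to the intention-to-treat set.

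**7. Does destruction cause the two results to merge?** If 0, 4, 8 or all 11 dropouts' records were destroyed (N = 23, m = 12), the carried-forward d_z would be 0.43, 0.48, 0.55 or 0.64. The observed-pairs figure does not move. Only loss of every dropout's record makes them equal, and people who simply stop responding are not covered by the withdrawal text at all.

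**The case for a change.** The strongest case for a change is that estimating effect sizes is a declared aim, that the plan itself treats leaving as informative, and that a choice made after seeing the data is open to selection. The arithmetic supports this as far as it goes. With completer d_z 0.64, 48% loss and no change in dropouts, a simulated 95% interval from observed pairs covers the mean change of all enrolled only 65% of the time at n = 54 (83% at n = 23). A later pre-post study at 80% power would need 22 people if sized on 0.64, and 81 if sized on 0.32. Giving observed-pairs and no-change results as a range restores coverage to about 98 to 99% in that case, for a few sentences of text.

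What stands is that the plan leaves the rule unwritten, and that it does not spell out the case of someone who withdraws and also asks for destruction. The information sheet and consent form (Appendices A and B) may do so; they are not in the text available.

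The rest carries less weight. No d_z, SD or f comes from the plan. The range performs well largely because f was taken between 0 and 1, the two assumptions that form its ends. At f = −0.5 its coverage falls to 90% (n = 23) and 75% (n = 54), and at f = 1.5 to 93% and 87%. The documents plan no later pre-post study. The range also consists of the two results that the promised analyses would most likely give anyway.

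**Conclusion.** No change is needed. The supposed contradiction does not hold: the withdrawal text is permissive and fits retention by default with destruction on request. It does not cause the two analyses to merge either.

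The missing rule for absent post scores is real, but it is a gap that analysts fill sensibly. With one post-baseline assessment and two analyses promised, baseline carried forward for intention-to-treat and observed pairs for completers is the most plausible reading. Readers would then see about 0.43 beside 0.64 at the attrition ceiling with 23 recruited. Which SD to divide by, and how to treat possible worsening among dropouts, are debatable refinements.

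The stakes are low. The effect size triggers no decision in an uncontrolled feasibility study judged on logins and guidance time, and at 12 pairs its interval spans about 0.00 to 1.25. This conclusion rests on an assumed completer d_z of 0.64 (0.3 to 1.0 examined), attrition up to 48%, and an analyst who does not present one set of pairs under both labels. If that last assumption failed, the equal sample sizes would show it in the report, provided each analysis is given with its n.
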